### Document revision history

Issue	Summary of change
01	New document

## Objectives

The aim of this study is to learn more about the microcirculation in the skin by examining sex and age-related day-to-day variability in healthy subjects.

## Design

Prospective observational study. In the study, four groups will be compared: Men aged 20-30 years, women aged 20-30 years, men aged 50-60 years and women aged 50-60 years. In total 48 participants will be included- 12 from each group.

## Background

The microcirculation consists of arterioles, capillaries and venules and is essential for nutrients and oxygen to be delivered to the tissue as well as waste products to be removed. The skin is often used as a model for studying the microcirculation.

Flowmotion is the rhythmical variations in measured skin blood flow that arise due to global and local regulations of the vessels and can be studied using frequency analysis of time-resolved blood flow signals.

There are many ways to study the microcirculation, most commonly are noninvasive optical techniques which measures the reflection of light used. In this study the single point technique EPOS and a larger area technique called PSI-X will be used. EPOS, based on laser doppler flowmetry (LDF) and diffuse reflectance spectroscopy (DRS), analyze speed-resolved perfusion, variations in red blood cell tissue fraction, oxygen saturation and vessel diameter. PSI-X, based on multi-exposure laser speckle contrast imaging (MELSCI) and multispectral imaging (MSI), analyze conventional perfusion, speed-resolved perfusion and oxygen saturation.

## Methods

To study day-to-day variability, each subject's data will be collected on two separate occasions within 7 days.

### Occasion 1

Once arriving to the lab, the subject will answer the following questions by filling in a questionnaire:

1. The subjects age and gender.
2. If the subject is biologically female- Usage of anticonception medication?
3. If the subject is biologically female- Number of days since the first day of the subject's period cycle, alternatively number of years since the subject's most recent period cycle?
4. How many minutes a week does the subject engage in high intensity workout (such as running, football ect)?
5. How many minutes a week does the subject engage in low intensity workout (such as hiking, biking, gardening work ect)?
6. Conformation to not have eaten two hours and not used nicotine, caffeine, or alcohol three hours prior to the experiment.
7. Conformation that the subject do not have a chronic disease such as diabetes, rheumatism ect.

Once the questions are filled in, the subject will receive information about the experiment and gets the opportunity to ask questions, thereafter a consent form is signed. The subject's height and weight will be measured and BMI calculated. The subjects skin type will be determined using the Fitzpatrick scale.

An acclimatization period of 15 minutes begins and the subject will remove socks and lay down. While the subject rests the equipment will be set up. A blood pressure cuff is placed around the upper arm as well as around the ankle. An EPOS-probe is placed on the dorsal side of the foot as well as the volar side of the forearm. A marker pen is used to mark the skin around the probes which enables the probe to be placed on the same location on the next measurement. A vacuum pillow is set up to position the arm and minimize movement artefacts. Once five minutes has passed, the subject's blood pressure and pulse are noted. Thereafter the PSI-X camera is set up and angled to film the plantar side of the foot from about 25 cm. The subject is asked to lay as still as possible during the measurement.

Once the acclimatization period has passed, the lights in the lab are turned off and the measurement will begin. Firstly, baseline data will be collected as the subject rest for 10 minutes without provocation. Thereafter the blood pressure cuff on the ankle will inflate to 250 mmHg for five minutes whilst data is collected. Lastly data is collected for five minutes after the blood pressure cuff deflates. Thereafter the PSI-X camera is moved and angled to film the forearm from a 25 cm distance. Baseline data will be collected on the arm as the subject rest for 10 minutes without provocation. Thereafter the blood pressure cuff on the upper arm will inflate to 250 mmHg for five minutes whilst data is collected and lastly data is collected for five minutes after the blood pressure cuff deflates. The temperature within the room is noted before and after the measurement.

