## **Occasion 2**

When arriving to the lab, the subject will confirm to not have eaten 2 hours and not have consumed caffeine or alcohol 3 hours prior to the experiment. Thereafter the subject will remove socks and lay down as the acclimatization period begins. A blood pressure cuff is placed around the upper arm as well as around the ankle. The EPOS-probes are placed within the marked skin areas from the previous measurement. A vacuum pillow is set up to position the arm and minimize movement artefacts. Once five minutes has passed, the subject's blood pressure and pulse are noted. Thereafter the PSI-X camera is set up and angled to film the plantar side of the foot from about 25 cm. The subject is asked to lay as still as possible during the measurement.

Once the acclimatization period has passed, the lights in the lab are turned off and the measurement will begin. Firstly, baseline data will be collected as the subject rest for 10 minutes without provocation. Thereafter the blood pressure cuff on the ankle will inflate to 250 mmHg for five minutes whilst data is collected. Lastly data is collected for five minutes after the blood pressure cuff deflates. Thereafter the PSI-X camera is moved and angled to film the forearm from a 25 cm distance. Baseline data will be collected on the arm as the subject rest for 10 minutes without provocation. Thereafter the blood pressure cuff on the upper arm will inflate to 250 mmHg for five minutes whilst data is collected and lastly data is

collected for five minutes after the blood pressure cuff deflates. The temperature within the room is noted before and after the measurement.

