## Statistical analysis of Day-to-day variability

Median values from the baseline data of each measurement will be extracted for all parameters. The maximum value during the post-occlusive reactive hyperemia (PORH) will also be extracted for all parameters. See Table 1 and Table 2 for more details regarding which values will be included in the data analysis.

*Table 1. Values extracted from the EPOS data of each measurement.*

Time period	Conventional perfusion	Speed-resolved-perfusion -Low speed	Speed-resolved-perfusion -Medium speed	Speed-resolved-perfusion -High speed	Oxygen saturation	Vessel diameter	RBC tissue fraction
Baseline of foot (10 minutes)	Median	Median	Median	Median	Median	Median	Median
Occlusion of foot (5 minutes)	No value extracted	No value extracted	No value extracted	No value extracted	No value extracted	No value extracted	No value extracted
PORH in foot (5 minutes)	Peak value	Peak value	Peak value	Peak value	Peak value	Peak value	Peak value
Baseline of arm (10 minutes)	Median	Median	Median	Median	Median	Median	Median
Occlusion of arm (5 minutes)	No value extracted	No value extracted	No value extracted	No value extracted	No value extracted	No value extracted	No value extracted
PORH in arm (5 minutes)	Peak value	Peak value	Peak value	Peak value	Peak value	Peak value	Peak value

*Table 2. Values extracted from the PSI-X camera of each measurement.*

Time period	Conventional perfusion	Speed-resolved-perfusion -Low speed	Speed-resolved-perfusion -Medium speed	Speed-resolved-perfusion -High speed	Oxygen saturation
Baseline of foot (10 minutes)	Median	Median	Median	Median	Median
Occlusion of foot (5 minutes)	No value extracted	No value extracted	No value extracted	No value extracted	No value extracted
PORH in foot (5 minutes)	Peak value	Peak value	Peak value	Peak value	Peak value
Baseline of arm (10 minutes)	Median	Median	Median	Median	Median
Occlusion of arm (5 minutes)	No value extracted	No value extracted	No value extracted	No value extracted	No value extracted
PORH in arm (5 minutes)	Peak value	Peak value	Peak value	Peak value	Peak value

To identify potential sex- and age-related variability, Wilcoxon test will be conducted for non-normally distributed data and t-test for normally distributed data. To compare the data collected from the foot to the arm, Kruskal-Wallis or Anova will be used.

Since multiple comparisons between groups will be conducted, Bonferroni corrections will be done to reduce the risk of Type 1 error.

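### The foot is always recorded before the arm, so a foot–arm comparison of levels cannot separate site from order, elapsed time and the preceding ankle occlusion

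*Protocol*

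**What the plan says.** **Sequence.** Protocol, Methods (Occasion 1) begins the recording with: "Firstly, baseline data will be collected as the subject rest for 10 minutes without provocation". The ankle cuff is then inflated for five minutes. The foot block closes with: "Lastly data is collected for five minutes after the blood pressure cuff deflates". The camera is moved to the forearm, and then: "Baseline data will be collected on the arm as the subject rest for 10 minutes without provocation". Upper-arm occlusion and recovery follow. Occasion 2 repeats this order, with the same hinge between the blocks: "Thereafter the PSI-X camera is moved and angled to film the forearm from a 25 cm distance". Neither document describes alternating or randomizing the order of the sites.

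**Set-up.** On Occasion 1, "An acclimatization period of 15 minutes begins and the subject will remove socks and lay down". Both EPOS probes are fitted in that period: "An EPOS-probe is placed on the dorsal side of the foot as well as the volar side of the forearm". Occasion 2 also places both probes before the first baseline. One PSI-X camera serves both sites in turn.

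**Analysis.** In the SAP, under Statistical analysis of Day-to-day variability, one sentence begins "To compare the data collected from the foot to the arm" and names Kruskal-Wallis or ANOVA. It mentions no term for order or time and no pairing within subject. Tables 1 and 2 take a median from each baseline and a peak from each post-occlusive (PORH) period, separately for foot and arm. Under Statistical analysis of Vasomotion data, the rows of Table 3, which are foot and arm periods, are introduced as the groups for comparison. The section ends by saying only that signals will for now be compared at group level.

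**Aim.** Protocol, Objectives: "examining sex and age-related day-to-day variability in healthy subjects".

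**The concern.** In a comparison of levels, each foot value is an early value and each arm value a late one, for every participant on both days. Any change in skin perfusion, saturation or vessel calibre with time at rest, and any response away from the ankle to the ankle occlusion, would add to the foot–arm difference. It could be read as a site effect, or it could hide a real one. More participants or a different test would not help, because the two explanations make the same prediction for the data as extracted. What is at stake is the conclusion about foot versus arm, which the SAP plans but the protocol's aim does not include.

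**Working it through.** The plan gives no figure for an order effect, so there is none to reproduce. The check has four parts.

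**1. Timeline.** Inputs from Protocol, Methods: baseline 10 min, occlusion 5 min, recovery 5 min, at each site. The camera move takes *g* min, which is not stated. Time is counted from the start of the foot baseline.

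| Period | Foot starts | Arm starts | Lag |
|---|---|---|---|
| Baseline | 0 | 10 + 5 + 5 + g = 20 + g | 20 + g |
| Occlusion | 10 | 20 + g + 10 = 30 + g | 20 + g |
| PORH | 15 | 30 + g + 5 = 35 + g | 20 + g |

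The lag is at least 20 min. For an assumed *g* of 2, 5 or 10 min it is 22, 25 or 30 min. The ankle cuff is released at 15 min, so the arm baseline begins 20 + g − 15 = 5 + g min later. On Occasion 1 the 15 min of acclimatization can be added. Counted from its start, the foot baseline begins at 15 min at the earliest and the arm baseline at 35 + g. Occasion 2 mentions acclimatization without giving its length, but the lag does not depend on it.

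Scheduled occlusions begun earlier in the session: none before the foot baseline and one before the arm baseline; one before the foot PORH (its own) and two before the arm PORH.

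**2. Can site and order be separated?** Take a linear model with intercept, site, order position and occasion, for 48 participants × 2 occasions × 2 sites. Under the fixed sequence the site and order columns are identical, and the design matrix has rank 3 out of 4. With order counterbalanced (24/24 between participants, or swapped between occasions) the rank is 4 out of 4. That result assumes an order effect common to both sites.

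**3. Levels or day-to-day differences?** Write the foot level as F, the arm level as A, and the order shift at the arm as δ.
- Levels: foot − arm = F − (A + δ) = (F − A) − δ. The shift stays in.
- Day 1 − day 2 within the arm, with day errors e1 and e2: (A + δ + e1) − (A + δ + e2) = e1 − e2. A constant δ cancels. Order then matters only if it differs between days or changes the spread.

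**4. Sensitivity, illustration only.** The documents give no δ and no SD. Assume no true site difference, n = 48, a paired t-test at an unadjusted two-sided 0.05, and an order shift of d SDs of the within-subject arm–foot difference (non-centrality d√48). The rejection rate is 5% at d = 0, 27% at 0.2, 53% at 0.3 and 92% at 0.5. These values of d are assumptions and not estimates.

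**What the EPOS set-up allows.** With arm readings from both windows,

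(foot early − arm late) = (foot early − arm early) − (arm late − arm early).

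This is exact for mean paired differences, though not for Kruskal-Wallis ranks. The last term is the order and time shift at the arm, and it can be measured if the arm probe records during the first window.

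**The case against.** The strongest reply is that a fixed order is good standardization for this study. The aim concerns day-to-day variability by sex and age. Comparing the same site across days, or between groups, sets like against like, because everyone follows the same sequence. That stands. A reader might infer that the fixed order undermines the study's main comparisons, but the documents do not support this.

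Second, the foot–arm sentence sits under a heading on day-to-day variability and may mean comparing variability between sites and not levels. This also stands: the SAP does not say which, and the point has full force only for levels.

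Third, no order effect has been shown. True. A reader might infer that the foot–arm result will be biased, or in which direction, but the documents give neither the existence nor the size of such an effect. The claim concerns separability alone. Acclimatization does not answer it, since it precedes both blocks and leaves the later lag and the ankle occlusion in place.

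Fourth, one camera forces sequential PSI-X recording. That explains why the sites are recorded in turn, but not why the foot must come first. A reader might therefore go too far the other way and call the PSI-X and PORH contrasts beyond repair; that holds only while the sequence is kept.

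Finally, the EPOS remedy depends on something the documents leave open: whether the arm probe records during the first baseline. Table 1 lists the arm baseline after the foot PORH row, so its natural reading is the later window. The earlier one would have to be added.

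**Conclusion.** The point holds, as a minor one. On both occasions every arm period starts at least 20 min after its foot counterpart and after an ankle occlusion. If the planned foot–arm comparison is of levels, site is fully aliased with order, elapsed time and prior occlusion. If it is of day-to-day differences, a constant shift cancels and little remains. Flowmotion contrasts between foot and arm rows may share the problem, given how the SAP introduces Table 3, although its closing sentence leaves the plan unclear.

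Confidence is high for non-separability of levels, which follows from the stated sequence. Nothing can be said from the documents about the actual size of any distortion. The consequence is confined to a comparison outside the stated aim.

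**What to change.** 1. **State the target.** Say in the SAP whether the foot–arm comparison concerns levels or day-to-day differences.
2. **EPOS baseline.** Confirm whether the arm probe records during the first 10-min window. If it does, take the foot–arm comparison from both probes in that window, before the ankle occlusion, and analyse it as a within-subject paired difference. Keep the later arm baseline for within-arm analyses. Report the mean paired late-minus-early arm difference as the order and time shift at the arm.
3. **Everything else.** For PSI-X, PORH and flowmotion foot–arm contrasts outside that window, and for the EPOS baseline if the arm probe did not record in it, report the level difference as site plus order. Draw no site conclusion while the fixed sequence is kept.

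Cost: SAP wording and one extra arm EPOS extraction, with no added visit and no change to the sequence if the arm probe already records. The downside is two arm EPOS baselines to label clearly and a narrower foot–arm conclusion. Counterbalancing the site order would make site and order separable with the same 48 participants, but it changes the procedure and is not needed for the stated aim.

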## Method for dealing with missing data

The goal is to have 48 complete set of data collection for the variability analysis and recruitment to the study will continue until this is achieved. Flowmotion analysis is more sensitive to artefacts, which most likely will be discovered late in the process once the recruitment to the study already is complete. Therefore we expect to exclude some measurements and most likely will not reach 48 complete sets of flowmotion signals.

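### Does recording room temperature at both visits without using it in the SAP undermine the day-to-day variability analysis?

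*Protocol*

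**What the plan says.** The Protocol's Objectives section aims at "examining sex and age-related day-to-day variability in healthy subjects". Under Design, "In total 48 participants will be included- 12 from each group", and under Methods each person's "data will be collected on two separate occasions within 7 days".

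For both Occasion 1 and Occasion 2 the Methods state: "The temperature within the room is noted before and after the measurement". No target temperature or permitted range is given. Conditions are standardised in other ways. At the first visit, "An acclimatization period of 15 minutes begins and the subject will remove socks and lay down", and socks come off and acclimatization is repeated at the second. Food, caffeine and alcohol are restricted before both visits, and the probes go back to marked skin sites.

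The SAP section on day-to-day variability extracts baseline medians and post-occlusion peaks from the two devices. On testing it says: "To identify potential sex- and age-related variability, Wilcoxon test will be conducted for non-normally distributed data and t-test for normally distributed data". Foot and arm are compared by Kruskal-Wallis or ANOVA. On multiplicity: "Since multiple comparisons between groups will be conducted, Bonferroni corrections will be done to reduce the risk of Type 1 error". No SAP section summarises room temperature, adjusts for it or excludes on it. The regression plots mentioned under visual presentation are not tied to any variable.

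**The concern.** Day-to-day variability is the quantity under study, and the investigators thought room temperature worth recording four times per participant. If skin blood flow responds to the room, a warmer second visit appears as within-person variation that has nothing to do with sex or age. The SAP does not say whether such variation belongs to the outcome or is noise to be removed.

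Three things could be at stake. Room differences could inflate within-person variation and cost precision. A group whose visits happened to span larger temperature changes could look more variable for a reason unrelated to sex or age. And an adjustment chosen after seeing the data would be post hoc across many parameters.

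**Working it through.** **Counts from the documents.** Readings: 48 participants × 2 visits × 2 = 192. Device values per visit: 7 parameters × 4 periods (SAP Table 1) + 5 × 4 (Table 2) = 28 + 20 = 48. The SAP gives no figure on temperature, so there is none to reproduce.

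**Which quantity is estimated.** The Protocol repeats the measurement on another day to study day-to-day variability, and the SAP adjusts for nothing. Followed as written, the plan yields total variation between days, room included. A room temperature shared by a participant's two visits cancels in the visit difference; only a change between visits remains.

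**Possible size, every input assumed.** Take a within-subject SD of 0.15 log units, a slope *b* of 0 to 0.10 log units per °C, and an SD *s* of the between-visit temperature difference of 0.5 to 2 °C. One SD cannot represent all parameters. The room's share of within-subject variance is

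(b·s)²/2 ÷ [0.15² + (b·s)²/2]

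| b | s | Share |
|---|---|---|
| 0 | any | 0% |
| 0.05 | 0.5 | 0.0003 / 0.0228 = 1.4% |
| 0.05 | 1 | 0.00125 / 0.02375 = 5.3% |
| 0.10 | 1 | 0.005 / 0.0275 = 18% |
| 0.10 | 2 | 0.020 / 0.0425 = 47% |

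**Would it mislead the group comparison?** Simulation with 40,000 runs, normal data, no true group difference and two-sided 0.05. The SAP defines no variability measure, so three readings were tried on visit differences: a t-test on signed differences, a t-test on absolute differences, and Brown-Forsythe, a test of spread that the SAP does not name.

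- Equal temperature spread in both groups (b = 0.10, 2 v 2 °C): all three reject in about 5% of runs or fewer.
- Worst case (b = 0.10, 1 v 2 °C): signed t-test 5% at 24 v 24 and at 12 v 12; Brown-Forsythe about 13% and 7%; absolute differences about 15% and 9%.
- Milder imbalance (b = 0.10, 0.5 v 1 °C): Brown-Forsythe 5% and 4%.

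These rates ignore the planned Bonferroni correction. The SAP does not give the number of comparisons. If it were six (all pairs of four groups, an assumption), the nominal level is 0.05/6 = 0.83%, and worst-case Brown-Forsythe gives 3.1% at 24 v 24 and 1.2% at 12 v 12. Some relative inflation remains, but only in that corner.

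**What adjustment would buy.** Regressing the visit difference on group and on the between-visit temperature difference uses one of 48 − 4 = 44 residual degrees of freedom. Critical t moves from 2.015 to 2.017. Residual variance falls only if the within-group |r| exceeds √(1/44) = 0.151. At s = 1 °C the SE of the slope is:

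- all 48: 0.15·√2/√44 = 0.032
- one group of 12: 0.2121/√11 = 0.064
- difference between two groups: 0.064·√2 = 0.090

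The last is close to the largest slope assumed, so 12 per group could hardly check the common slope that the model needs. A table of between-visit changes by group would also show only gross imbalance: the 95% interval for a ratio of two groups' temperature SDs runs from 0.54 to 1.86 times the observed ratio at 12 v 12.

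**The case for a change.** The best case for a change is that it is nearly free. One sentence could call the target total day-to-day variability, one table could show temperature by visit and group, and the role of a recorded variable would be settled before the data are seen. Because no temperature range is set, the room is less controlled than food, caffeine or probe position. The SAP also says "The goal is to have 48 complete set of data collection for the variability analysis" and that recruitment continues until then, so one group may be completed later than the others. In the worst case above, a real excess in total variability would come from the room and be read as an effect of sex or age.

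The facts behind this stand, and a temperature table would be good reporting. It does not follow that the plan is wrong. A group completed later may be measured at a different temperature level, but that cancels in the visit difference; what matters is unequal change within a participant's own seven days. If the tests are instead taken to compare levels, a group difference in room temperature would matter, but nothing in the documents points to one. The label and the table alter no planned result. The adjusted model rests on a variability measure that the SAP has not defined. That is a separate and larger gap, and until it is settled the form of any adjustment is undetermined. Temperature is not special either: blood pressure and pulse at both visits, BMI, skin type, exercise and menstrual timing are also collected without a stated role.

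**Conclusion.** No change is needed. Room temperature is recorded at both visits and has no role in the SAP, so the day-to-day differences may include room conditions. Under the natural reading of the objective, total variation between two days, the unadjusted analysis is the right one. Bias between groups would need a sizeable temperature effect together with unequal between-visit temperature change, and the documents indicate neither. The size is unknown: 0% to 47% of within-subject variance on wholly assumed inputs, and possibly negligible. The raised rejection rates appear only at the extreme of those inputs and with a measure or test that the SAP does not specify. Since the readings are collected, an analyst can tabulate them in the report and treat any temperature-adjusted analysis as exploratory. The conclusion would change if the stated target were variability at fixed room conditions, or if groups were scheduled under systematically different room conditions.
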